**NCT03097549**

**Document Date: January 4, 2017**

**Updated with Title Page 18/02/2025**

## Tät II clinical trial: Study Protocol

### Summary

The purpose of this study is to determine the short-term effect of self-management of mixed urinary incontinence (MUI) and urgency urinary incontinence (UUI) via a mobile app.

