### Description

Female urinary incontinence (UI) is common and affects up to one fourth of adult women (1). It may reduce quality of life for those affected and costs for society are high. The most common type of urinary incontinence is stress urinary incontinence (SUI), i.e. leakage when coughing, sneezing or jumping. UUI, i.e. a strong urge to urinate combined with leakage and MUI, i.e. a combination of both types, together adds up to nearly half of the cases of UI in women (1). Many women do not seek care, sometimes due to embarrassment (2). The recommended first line treatment for all types of UI is pelvic floor muscle training (PFMT) in combination with lifestyle changes. This treatment leads to improvement or cure in two-thirds of patients. In addition, bladder training might be effective in treatment of UUI and MUI, leading to improvement or cure in one-sixth of treated women with MUI (3,4). Research also suggests that psychological treatment might be valuable for some women with UUI or MUI (5).

The use of smartphones is increasing rapidly. About 81% of all cell phones in Sweden today (in 2017) are smartphones. The majority of adults in Sweden own a smartphone. Many smartphone owners have at least one health app on their phone. Exercise, diet, and weight apps are the most popular types.

There is a need for new, flexible and easily accessible treatment programmes for female urinary incontinence. The investigators have previously demonstrated the efficacy of the mobile app Tät® for treatment of SUI (6). Apps have the potential to improve symptoms in many chronic conditions through self-management interventions (7).

From our previous experience of a smartphone app treatment for SUI, we have developed a new app combining some of the features from the previous app with new features more specifically aimed towards treatment of UUI and MUI. The effect of the treatment programme will be evaluated after three months by comparing the effect in a group which receives the full contents of the new app (the “treatment app group”) with a group which initially receives a limited version of the app containing only brief information and no actual exercises (the “information app group”).

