## Procedure

Participants are consecutively recruited through our website [tät.nu](http://tät.nu). They answer an online screening survey with automated immediate response for initial screening of eligibility criteria. Informed consent and leakage diary (number of episodes of urinary leakage during 48 hours) are sent by post. After that, they answer a web questionnaire and finally they are interviewed by a researcher to confirm the diagnosis UUI or MUUI, to discover any alarm symptoms motivating directing the participant to other care, and to ascertain that the patient is well informed of the study procedure. Women are then randomized to either of the two groups. Women in both groups get a smartphone application for iPhone or Android. The treatment app group receives a unique code for activation of the complete app. Follow-up after three months with a web questionnaire and a leakage diary. After that the information app group get their unique activation code.

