## Eligibility

### Inclusion Criteria

- age 18 years or older
- female
- urge urinary incontinence or mixed urinary incontinence
- leakage twice a week or more often
- duration of symptoms for at least 12 months
- motivation and time to perform a 12-week treatment with pelvic floor muscle training
- ability to read and write Swedish
- access to smartphone/tablet
- possibility to send and receive email and asset to printer
- accept to be randomized to one of two groups; a treatment app group or an information app group

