### Primary outcome

Comparison between groups:

The primary outcome is the difference between the groups in mean ICIQ-UI SF score change from baseline to 15-weeks follow-up. This will be compared using a linear mixed models analysis.

Comparison within groups:

For comparison within the groups regarding the change in ICIQ-UI SF score from baseline to 15-weeks follow-up, a paired t-test will be used.

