## Outcome Measures

### 1. Primary Outcome Measure

Measure Title	International Consultation on Incontinence Modular Questionnaire Urinary Incontinence Short Form (ICIQ-UI SF)
Measure Description	Three items on frequency, amount of leakage and overall impact. Scoring 0-21, higher values indicating increasing severity

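### The plan names urgency and mixed incontinence and establishes each woman's type before randomisation, but does not use it in any stated stratification or analysis, so the pooled primary result cannot by itself show benefit in urgency incontinence

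*Combined protocol and SAP*

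**What the plan says.** - **Purpose and population.** The protocol Summary gives the aim as the "short-term effect of self-management of mixed urinary incontinence (MUI) and urgency urinary incontinence (UUI) via a mobile app". The Inclusion Criteria admit "urge urinary incontinence or mixed urinary incontinence", with no quota for either type.
- **What MUI is.** The Description describes "MUI, i.e. a combination of both types", that is, stress plus urgency leakage.
- **The app.** The Description reports that the sponsor's earlier app worked in stress incontinence and says the new one combines some of its features with others directed at UUI and MUI. It names pelvic floor muscle training (PFMT) as first-line treatment for every type of incontinence. The Intervention section lists PFMT, bladder training and psychological exercises.
- **Type is known in time.** Under Procedure, "finally they are interviewed by a researcher to confirm the diagnosis UUI or MUUI" (I read the last abbreviation as MUI). The next step is "Women are then randomized to either of the two groups". Neither Procedure nor Study Design gives an allocation method or a stratification factor.
- **Primary analysis.** The SAP compares "the difference between the groups in mean ICIQ-UI SF score change from baseline to 15-weeks follow-up" by a linear mixed model. Type does not appear there or under Secondary outcomes.
- **Outcomes.** The primary score has "Three items on frequency, amount of leakage and overall impact". The weekly episode count is not split by leak type. ICIQ-OAB, a secondary outcome, covers day and night micturition frequency, urgency and urgency leakage, and is compared between the whole groups.

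**The concern.** The purpose names two conditions, and the plan yields one difference averaged over both. Women with MUI have a stress component. The app contains a treatment that the protocol regards as effective for stress leakage, and the primary score counts a stress leak like any other. A positive pooled result could therefore reflect benefit in both types, or benefit mainly in MUI, and the primary analysis would look the same either way.

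The assumed effect adds some weight to this. Under Sample size it rests on two sources, one of which is the trial of the earlier app in stress incontinence.

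What is at stake is attribution, not the validity of the primary test. Readers will want to know whether the app helps women with UUI alone. The plan collects the variable needed to address this and then leaves it unused.

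**Working it through.** **Inputs from the Sample size section:** improvement of 2.5 points (treatment) and 0.9 (control); 80% power; two-sided 0.05; 49 per group; 20% dropout; about 60 per group.

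**Not in the documents:** the SD and the UUI share *u*. The SD is solved back from the plan's 49; *u* is assumed to be 20-50%.

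**1. The plan's own figure.** The difference is 2.5 − 0.9 = 1.6. The 49 cannot be derived without an SD, so solve for it:

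SD = 1.6 × √(49/2) / (1.960 + 0.842) = 2.83 (2.80 by the t-test version).

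An SD of about 2.8 thus reproduces 49. For dropout, 49/0.8 = 61.25, in line with approximately 60.

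**2. Pooled difference.** With the same *u* in both arms, pooled = *u* × (UUI effect) + (1 − *u*) × (MUI effect). If the UUI effect is zero and the pooled value is 1.6, the MUI effect must be 1.6/(1 − *u*). Adding the control improvement of 0.9, assumed equal in both types, gives the total improvement that treated MUI women would need.

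**3. Precision within UUI.** With 49*u* women per arm, the 95% half-width is 1.96 × 2.83 × √(2/(49*u*)).

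| Assumed *u* | MUI effect needed | Treated MUI women's total improvement | UUI women per arm | UUI 95% half-width |
|---|---|---|---|---|
| 20% | 2.00 | 2.9 | 9.8 | 2.50 |
| 30% | 2.29 | 3.2 | 14.7 | 2.04 |
| 40% | 2.67 | 3.6 | 19.6 | 1.77 |
| 50% | 3.20 | 4.1 | 24.5 | 1.58 |

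**4. Power at SD 2.83 and 49 per arm.** The standard errors are 2.83 × √(2/49) for the pooled difference, 2.83 × √(2/(49*u*)) within UUI, and 2.83 × √(2/(49*u*) + 2/(49(1 − *u*))) for the interaction.

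| Assumed *u* | Pooled test significant if MUI effect 1.6, UUI effect 0 | UUI-only test, true effect 1.6 | Interaction of 1.6 points |
|---|---|---|---|
| 20% | 61.1% | 24.0% | 20.1% |
| 30% | 50.0% | 33.5% | 24.9% |
| 40% | 39.0% | 42.5% | 27.8% |
| 50% | 28.8% | 50.8% | 28.8% |

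**5. Chance imbalance, only if allocation is simple.** Take two independent Binomial(60, *u*) counts. A gap of 10 percentage points is 6 women, and P(|difference| ≥ 6) = 0.21, 0.27, 0.31 and 0.32 for *u* = 20, 30, 40 and 50%.

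**The case against.** The case for the plan is substantial.

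- **The pooled comparison answers a legitimate question.** There is one population, one app, one effect size and one primary comparison. Randomisation makes that comparison unbiased for the combined population, and the plan nowhere promises separate efficacy in each type. This stands.
- **A reader might infer that a positive result would be merely a stress effect.** The documents do not support that. They call PFMT first-line for all types, and the app adds bladder training and features directed at UUI and MUI. At UUI shares of 40-50% the scenario needs a net MUI effect of 2.7-3.2 points, above the 2.5-point total improvement assumed for the treatment arm. Zero UUI effect is possible, but nothing makes it likely.
- **Urgency is measured.** ICIQ-OAB has no stress item as described, so a gain on the primary score without one on ICIQ-OAB would be a warning. This stands in part: ICIQ-OAB is pooled too, so a gain on it could come from the urgency component in MUI women.
- **A reader might also infer simple randomisation and a real risk of unequal arms.** The documents give no allocation method. The 21-32% figure is conditional, chance imbalance does not bias a randomised test, and nothing in the documents quantifies how far type predicts outcome. The planned baseline comparison of incontinence-related parameters could include type.
- **Analyses by type will be weak.** This is correct. With a true UUI effect of zero, the estimate would still favour the app about half the time, so its direction says little. This limits what the fix can deliver, but is not a reason to leave type unused.

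**Conclusion.** The point holds in a limited form. The primary test is sound for the combined UUI/MUI population. On its own it cannot show benefit in UUI, and no planned analysis uses the type that the interview establishes. ICIQ-OAB softens this without removing it.

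As an illustration, a pooled 1.6 is compatible with zero UUI effect if the MUI effect is 2.0-3.2 points, for assumed UUI shares of 20-50%; the upper end is large against the plan's assumptions. These figures show what is arithmetically possible, not what is likely. They rest on the assumed share, and the precision and power figures also rest on the back-solved SD, taken as equal in both types. The central argument needs neither: it follows from the definition of MUI, the content of the score and the absence of type from the SAP.

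It would go too far to conclude that the design is biased or fails its stated purpose. This is an inexpensive improvement worth making.

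**What to change.** 1. **Procedure:** stratify randomisation by interview-confirmed type (UUI or MUI), for example with permuted blocks. If allocation is already stratified, say so.
2. **SAP, Primary outcome:** include type as a factor in the primary model. If the mixed model takes both baseline and follow-up scores as responses, add type-by-visit, because a main effect of type alone would not adjust the change.
3. **SAP, Primary and Secondary outcomes:** pre-specify, for ICIQ-UI SF and ICIQ-OAB, the between-group difference with 95% CI within UUI and within MUI, and the treatment-by-type interaction. Label these as exploratory estimation.
4. **Conclusion:** state that the primary conclusion refers to the combined UUI/MUI population.

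The cost is two allocation lists instead of one and a few lines in the SAP, with no new data and no extra participants. If allocation is already complete, items 2-4 remain possible.

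The downside is wide intervals: about ±1.6 to ±2.5 points in UUI at 49 evaluable per arm. The SAP should say that the interval, not the direction of the estimate, will be interpreted, and that a null UUI result is not evidence of no effect. Powering UUI alone is out of proportion: keeping 49 UUI women per arm would take 49/*u*, or 98 (50% UUI) to 245 (20% UUI) evaluable women per arm.

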### Description

Female urinary incontinence (UI) is common and affects up to one fourth of adult women (1). It may reduce quality of life for those affected and costs for society are high. The most common type of urinary incontinence is stress urinary incontinence (SUI), i.e. leakage when coughing, sneezing or jumping. UUI, i.e. a strong urge to urinate combined with leakage and MUI, i.e. a combination of both types, together adds up to nearly half of the cases of UI in women (1). Many women do not seek care, sometimes due to embarrassment (2). The recommended first line treatment for all types of UI is pelvic floor muscle training (PFMT) in combination with lifestyle changes. This treatment leads to improvement or cure in two-thirds of patients. In addition, bladder training might be effective in treatment of UUI and MUI, leading to improvement or cure in one-sixth of treated women with MUI (3,4). Research also suggests that psychological treatment might be valuable for some women with UUI or MUI (5).

The use of smartphones is increasing rapidly. About 81% of all cell phones in Sweden today (in 2017) are smartphones. The majority of adults in Sweden own a smartphone. Many smartphone owners have at least one health app on their phone. Exercise, diet, and weight apps are the most popular types.

There is a need for new, flexible and easily accessible treatment programmes for female urinary incontinence. The investigators have previously demonstrated the efficacy of the mobile app Tät® for treatment of SUI (6). Apps have the potential to improve symptoms in many chronic conditions through self-management interventions (7).

From our previous experience of a smartphone app treatment for SUI, we have developed a new app combining some of the features from the previous app with new features more specifically aimed towards treatment of UUI and MUI. The effect of the treatment programme will be evaluated after three months by comparing the effect in a group which receives the full contents of the new app (the “treatment app group”) with a group which initially receives a limited version of the app containing only brief information and no actual exercises (the “information app group”).

### Intervention and control

#### Intervention: Tät II treatment app

Smartphone treatment with various exercises: A smartphone application with information on UUI/MUI, lifestyle information, psychological education and exercises, different programmes of PFMT and Bladder Training with increasing challenges, statistics on training. Possibility to set reminders. The treatment period is 15 weeks, and after that, maintenance training is recommended.

#### Control: Information app

Limited version of app, containing brief information, for three months. They receive the activation code for the treatment app after follow-up.

## Study Design

Study Type: Interventional

Primary Purpose: Treatment

Interventional Study Model: Parallel Assignment, 2 arms

Masking: No masking

Allocation: Randomized

Time to follow-up: 15 weeks

## Procedure

Participants are consecutively recruited through our website [tät.nu](http://tät.nu). They answer an online screening survey with automated immediate response for initial screening of eligibility criteria. Informed consent and leakage diary (number of episodes of urinary leakage during 48 hours) are sent by post. After that, they answer a web questionnaire and finally they are interviewed by a researcher to confirm the diagnosis UUI or MUUI, to discover any alarm symptoms motivating directing the participant to other care, and to ascertain that the patient is well informed of the study procedure. Women are then randomized to either of the two groups. Women in both groups get a smartphone application for iPhone or Android. The treatment app group receives a unique code for activation of the complete app. Follow-up after three months with a web questionnaire and a leakage diary. After that the information app group get their unique activation code.

## Monitoring

The study will be monitored according to GCP principles by study research nurse [name] at the local clinical research centre of the Region of Jämtland Härjedalen to ascertain a proper procedure of conduction, recording and reporting data. The monitor will review study records, observe protocol procedures and the randomization process, ensure that written informed consent has been correctly obtained and verify patient safety by monitoring the correct reporting of any adverse events.

## Sample size

Based on previous results from our study and the findings of Albers-Heitner et al (6, 8), we assume an improvement in the ICIQ UI SF of 2.5 p in the treatment app group and 0.9 p in the information app group. To detect this difference with 80% power, 2-side test and significance 0.05, we need a sample size of 49 in each group. With an expected drop-out rate of 20%, we need approximately 60 participants in each group. We therefore aim to recruit 120 women aged 18 and older via our website [www.tät.nu](http://www.tät.nu).

## Eligibility

### Inclusion Criteria

- age 18 years or older
- female
- urge urinary incontinence or mixed urinary incontinence
- leakage twice a week or more often
- duration of symptoms for at least 12 months
- motivation and time to perform a 12-week treatment with pelvic floor muscle training
- ability to read and write Swedish
- access to smartphone/tablet
- possibility to send and receive email and asset to printer
- accept to be randomized to one of two groups; a treatment app group or an information app group

### Exclusion Criteria

- participation in our previous internet study or smartphone study
- pregnancy
- former incontinence surgery
- known malignancy in lower abdomen
- unassessed difficulties in emptying bladder
- visual blood in urine
- three or more urinary tract infections within the last year or pyelonephritis in the last three years
- painful urgency
- intermenstrual bleeding
- neurological disease with affection on sensibility in legs or lower abdomen
- Usage of the previous app Tät® during the last month
- Usage of anticholinergic drugs during the last month
- Maximum urinary volume of less than 100 ml
- Need for further assessment of symptoms, based on a telephone interview performed by an experienced urotherapist

## Tät II clinical trial: Statistical analysis plan

Intention-to-treat analysis will be performed on all outcome measures.

### Baseline comparison

The two groups will be compared at baseline regarding demographic factors and incontinence-related parameters:

For continuous variables, Student's t-test will be used.

For categorical variables, Pearson's chi-square test will be used.

For ordinal variables, and continuous variables with a non-normal distribution, the Mann-Whitney U-test will be used.

### Primary outcome

Comparison between groups:

The primary outcome is the difference between the groups in mean ICIQ-UI SF score change from baseline to 15-weeks follow-up. This will be compared using a linear mixed models analysis.

Comparison within groups:

For comparison within the groups regarding the change in ICIQ-UI SF score from baseline to 15-weeks follow-up, a paired t-test will be used.

### Secondary outcomes

Comparison between groups:

For the secondary outcomes the difference between the groups in mean ICIQ-LUTSqol, ICIQ-OAB and Incontinence Catastrophizing Scale (ICS) score changes from baseline to follow-up, a linear mixed models analysis will be used.

For the secondary outcome the difference between the groups in the median value of Patient's Global Impression of Improvement (PGI-I), a question on improvement only used at follow-up, the Mann-Whitney U-test will be used.

For the secondary outcome the difference between the groups in the median Incontinence Episode Frequency (IEF) from baseline to follow-up, the Mann-Whitney U-test will be used.

For the secondary outcome the changes in usage of incontinence aids from baseline to follow-up, we will use a six-item question about the frequency of usage in the last four weeks. We will compare the groups using the Mann-Whitney U-test.

Comparison within groups:

For comparison within the groups regarding the change in ICIQ-LUTSqol, ICIQ-OAB and ICS scores from baseline to 15-weeks follow-up, a paired t-test will be used.

For comparison within the groups regarding the change in IEF and incontinence aid usage from baseline to 15-weeks follow-up, a Wilcoxon signed-rank test will be used.

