### 6. Secondary Outcome Measure:

Measure Title	Change from baseline Usage of incontinence aids at 15 weeks
Measure Description	Use of incontinence aids during the last four weeks, six response options from "Never" to "more than one incontinence aid per day"

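### The between-group test on change in incontinence-aid use is valid but does not condition on the baseline category; adjusting for it would gain some power on this secondary outcome at almost no cost

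*Combined protocol and SAP*

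**What the plan says.** The SAP, under Secondary outcomes (comparison between groups), introduces the outcome with "For the secondary outcome the changes in usage of incontinence aids from baseline to follow-up" and then states "We will compare the groups using the Mann-Whitney U-test". It names no covariate, stratification, ordinal model or effect estimate for this outcome.

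Item 6 under Outcome Measures is titled "Change from baseline Usage of incontinence aids at 15 weeks" and described as "Use of incontinence aids during the last four weeks, six response options". The SAP text speaks of six items, but the Outcome Measures entry makes clear that this is one question with six ordered answers.

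For the within-group comparison the SAP writes "regarding the change in IEF and incontinence aid usage from baseline to 15-weeks follow-up, a Wilcoxon signed-rank test will be used".

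No sentence says outright which variable enters the Mann-Whitney test. The references to change, the title of item 6 and the signed-rank test, which needs individual differences, make the difference in category the natural reading.

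**The concern.** A difference in category codes uses the baseline by subtraction, but it does not compare women who started from the same place. Three things follow.

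- The difference carries the full variability of the baseline answer. When baseline and follow-up are only moderately correlated, that costs precision.
- Every one-step move counts the same, wherever on the scale it starts.
- Room to move differs by starting category. The eligibility criteria require leakage at least twice a week but set no minimum aid use, so women in the lowest category can be enrolled and can only stay put or worsen. The top category is open-ended, so a reduction within it scores zero.

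At stake is the precision of one randomised secondary comparison. The SAP models change in ICIQ-LUTSqol, ICIQ-OAB and ICS with linear mixed models. The aid item is also measured at baseline but gets only an unadjusted rank test.

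**Working it through.** **1. The plan's own figures.** Power is planned only for ICIQ-UI SF: "To detect this difference with 80% power, 2-side test and significance 0.05", with assumed improvements of "2.5 p in the treatment app group and 0.9 p in the information app group". The difference is 2.5 − 0.9 = 1.6 points. No SD is given. Solving n = 2·SD²·(1.96 + 0.84)²/1.6² for n = 49 gives SD = 1.6·√(49/(2 × 7.85)) ≈ 2.83, so 49 per group is consistent with an SD of about 2.8 but cannot be checked further. For dropout, 49/0.80 = 61.25, against the stated figure of about 60; conversely 60 × 0.80 = 48 women with follow-up. The aid item has no stated effect, distribution, correlation or power.

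**2. Analytic comparison.** Let ρ be the correlation between the analysed baseline and follow-up scores, with equal variances σ². The variance of a change score is 2σ²(1 − ρ), and that of a baseline-adjusted score is σ²(1 − ρ²). The ratio of adjusted to change is (1 + ρ)/2. If the adjusted analysis has 80% power (1.96 + 0.84 = 2.80), the change-score power is Φ(2.80·√((1 + ρ)/2) − 1.96). At ρ = 0.5 this is Φ(2.426 − 1.96) = 67.9%, a loss of 12 points.

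| ρ | Change-score power | Loss (points) |
|---|---|---|
| 0.1 | 54.7% | 25 |
| 0.3 | 61.7% | 18 |
| 0.5 | 67.9% | 12 |
| 0.7 | 73.3% | 7 |
| 0.8 | 75.7% | 4 |

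**3. Simulation under the planned missing-data rule.** The SAP's Missing data section replaces a missing follow-up value with the baseline value. This raises the correlation in the analysed data: in one scenario the observed correlation rose from 0.24 with complete data to 0.39 with 20% imputed. The simulation cut a latent bivariate normal into six categories, with 60 women per arm and 20% of follow-up values imputed as no change. Category distributions, latent correlations and shifts are all assumptions. For a U-shaped distribution and a latent shift of 0.5 SD:

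| Latent correlation | Mann-Whitney on change | Rank ANCOVA | Gain (points) |
|---|---|---|---|
| 0.3 | 38.9% | 57.0% | 18.1 |
| 0.5 | 50.6% | 64.4% | 13.8 |
| 0.7 | 65.2% | 75.8% | 10.6 |
| 0.8 | 79.7% | 88.0% | 8.3 |
| 0.9 | 93.8% | 97.3% | 3.5 |

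Over four assumed distributions at the same shift, the gain was about 14 to 18 points at 0.3, 9 to 17 at 0.5, 5 to 11 at 0.7 and 3 to 10 at 0.8. A separate run with one assumed distribution gave about 18, 17, 13, 6 and 4 points at 0.3, 0.5, 0.7, 0.8 and 0.9. Gains can be negligible. With evenly spread categories and proportional-odds adjustment, power went from 26.4% to 26.6% at correlation 0.8 and a 0.2 SD shift, and was 100% for both methods at correlation 0.9 and a 0.7 SD shift. Monte-Carlo error is about 1 to 3 points per cell.

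**4. Validity.** With no true effect, the Mann-Whitney test on change rejected in 3% to 6% of simulated trials.

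**5. The other reading.** If only follow-up categories were compared, the unadjusted test in the U-shaped case would have 49.7% power at correlation 0.3 and 49.0% at 0.8, against 57.0% and 88.0% with adjustment. The loss differs in size, but adjustment is still the better choice.

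**The case against.** Mann-Whitney is a conventional choice for an ordinal item and fits the SAP's stated handling of ordinal variables. It controls type I error, and the outcome is one of several secondaries with no power target. All of that stands.

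A reader might also go further than the documents allow:

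- *That the baseline is ignored.* It is not: a change score uses it by subtraction. What is missing is conditioning on it.
- *That the trial loses a fixed and large amount of power, say 12 to 25 points.* In step 2 that range needs ρ between 0.5 and 0.1. The documents give no correlation, a habitual behaviour asked about twice in 15 weeks could correlate more strongly, and the missing-data rule pushes the correlation up.
- *That adjustment cures the floor.* A woman in the lowest category cannot improve under any analysis of this item. Adjustment only compares her with women who started where she did.
- *That the planned test cannot give an effect size.* It has one, the probability of superiority. The SAP's silence on this is a reporting gap, not a fault of the test.

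The spacing criticism also reaches the alternatives in part. Rank ANCOVA assumes linearity in the baseline ranks. A proportional-odds model needs either a scored baseline, which brings spacing back, or five indicators fitted to about 100 to 120 women. The coding therefore has to be stated in advance.

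**Conclusion.** The point holds as one of efficiency, not of validity. On the natural reading, the planned test compares differences in category without conditioning on a baseline that is already collected. Rank ANCOVA and baseline-adjusted proportional odds were at least as powerful in every simulated scenario with an effect.

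Under the planned imputation the gain runs from about 0 to 18 points. It is largest at low-to-moderate correlation and small at 0.8 to 0.9. That range rests on assumed category distributions, shifts and correlations, and on 20% missing follow-up taken from the protocol's dropout figure; it is not a property of this trial that can be read off the documents. The documents do not support a conclusion that the planned result would be biased or that the primary analysis is affected. The change is optional.

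**What to change.** In the SAP, under Secondary outcomes, make the between-group analysis of aid use a comparison of the 15-week category adjusted for the baseline category. Two forms are suitable:

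- rank ANCOVA, which needs no proportional-odds assumption; or
- proportional-odds regression with arm and baseline category, stating how baseline is coded (score or indicators) and reporting the odds ratio with its 95% CI.

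Keep the Mann-Whitney test as a sensitivity analysis, and say whether it is applied to the change or to the follow-up category.

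The cost is one or two sentences and no new data. The regression adds a proportional-odds assumption; it converged in all simulated trials at 49 to 60 per group.
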